# Design

Intervention development, piloting and cluster randomised controlled exploratory trial (MRC complex intervention phase II trial). Two drug prevention interventions (ASSIST+Frank and Frank friends) will be developed using the peer nomination and training manual from an existing effective peer-led smoking prevention intervention, ASSIST; content on drug misuse will come from the UK national drug education service, "Frank". (www.talktofrank.com). ASSIST+Frank and Frank friends will be piloted in one school each and be followed by a process evaluation and period of intervention refinement. A 4-arm cluster exploratory RCT (ASSIST in year 8 with ASSIST+Frank adjunct intervention in year 9; ASSIST in year 8 only; Frank friends in year 9 only; usual care comparison) will then be conducted, with an embedded process evaluation

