# 6 Study design

This proposed project has 3-stages (see above study schema on page 14):

Stage 1: Development of training materials and an intervention manual for ASSIST+Frank and Frank friends;

Stage 2: Piloting of ASSIST+Frank in one school and Frank friends in one school followed by a period of refinement of the interventions;

Stage 3: Exploratory 4-arm trial with cluster randomisation (at the level of school) in 12 state secondary schools in South Wales with an embedded process evaluation.

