# 8.1 Progression criteria

Within the exploratory trial, a process evaluation will inform assessment against the following progression criteria (to be agreed in advance by the Trial Steering Committee):

Acceptability and feasibility of the interventions to school and intervention delivery staff

- 1. Was it feasible to implement the ASSIST+Frank intervention in (at least) 2 out of 3 intervention schools? This will be assessed according to whether: a) 75%+ of year 8 ASSIST peer supporters are recruited and re-trained as ASSIST+Frank peer supporters in year 9; b) 75%+ of year 9 students nominated are recruited and trained as Frank friends peer supporters and, c) PHW staff delivered the additional ASSIST+Frank training in full in all 3 intervention schools. This will be assessed via interviews and focus groups with peer supporters and PHW staff, as well as observations of peer supporter training.
- 2. Was it feasible to implement the Frank friends intervention in (at least) 2 out of 3 intervention schools? This will be assessed according to whether: a) PHW staff delivered the Frank friends training in full in all 3 schools. This will be assessed via interviews and focus groups with peer supporters and PHW staff, as well as observations of peer supporter training.

Acceptability of the intervention to peer supporters and fidelity

- 3. Was the intervention acceptable to students trained as ASSIST+Frank peer supporters? This will be assessed according to whether: a) 75%+ of ASSIST+Frank peer supporters report having at least 1 or more informal conversations with their peers at school about drug-related risks/harms; and b) 75%+ of ASSIST+Frank peer supporters report at least one contact with PHW staff, either via a follow-up visit and/or contact via email, text or Facebook. This will be assessed via interviews and focus groups with peer supporters and PHW staff, and analysis of documentary evidence (e.g. PHW log of attendance at follow-ups, etc.).
- 4. Was the intervention acceptable to students trained as Frank friends peer supporters? This will be assessed according to whether: a) 75%+ of Frank friends peer supporters report having at least 1 or more informal conversations with their peers at school about drug-related risks/harms; and b) 75%+ of Frank friends peer supporters report on-going contact with PHW staff throughout the year via a follow-up visit. This will

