be assessed via interviews and focus groups with peer supporters and PHW staff, and analysis of documentary evidence (e.g. PHW log of attendance at follow-ups, etc.).

Acceptability of the intervention to school staff and parents

- 5. Was the ASSIST+Frank intervention acceptable to the majority of school senior management teams (SMT), other school staff, and parents? This will be assessed via interviews with SMT and focus groups with school staff and parents.
- 6. Was the Frank friends intervention acceptable to the majority of school senior management teams (SMT), other school staff, and parents? This will be assessed via interviews with SMT and focus groups with school staff and parents.

Acceptability of the trial design and assessment methods

7. Were the trial design and methods acceptable and feasible? This will be assessed according to whether: a) randomization occurred as planned and was acceptable to SMTs; b) a minimum of 5 out of 6 intervention schools and 2 out of 3 schools from the comparison arms participate up in the 18 month follow-up? and, c) the student survey response rates are acceptable at baseline (80%+) and follow-up (75%+).

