#### 9.6 Randomisation

In the exploratory trial, randomisation of schools will occur after all schools have completed baseline data collection. Schools will be randomly assigned to one of the 4 arms with an assignment ratio of 3: 3: 3: 3. Allocation will be conducted by an independent SEWTU statistician, blind to the identity of schools, and minimised on: the percentage of pupils in receipt of free school meals and school size to balance the randomisation. Optimal allocation will be used to carry out the randomisation. Here a balance algorithm is used when predefined sequence generation is required or when all units are randomised jointly. Data on school size and free school meal entitlement will be collected at recruitment and used to balance the randomisation.

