11.1.4 Usual care

The three schools that do not receive ASSIST, ASSIST+Frank or Frank friends will continue

their usual activities. These may or may not involve education on smoking or drug use.

12 Adverse Events

Adverse Event (AE): Any untoward medical occurrence in a trial participant which does not

necessarily have a causal relationship with the intervention. An AE can therefore be any

unfavourable and unintended sign (including abnormal laboratory finding), symptom, or

disease. Within this study, this may include a young person revealing incidences of self-

harm, sexual abuse, and grooming by being provided drugs.

**Serious Adverse Event (SAE):** Any adverse event that:

• Results in death

• Is life-threatening

• Required hospitalisation or prolongation of existing hospitalisation

• Results in persistent or significant disability or incapacity

• Consists of a congenital anomaly or birth defect

• Other medically important condition

**Expected AE/SAE:** There are no expected AE's/SAE's. Any planned treatments received by

participants at the start of the study, will not be considered as AE's/SAE's.

**Related AE/SAE**: The AE/SAE resulted from administration of any of the research procedures (causal to the research process or intervention).

There are no AE's/SAE's expected to be related specifically to the study interventions. All intervention materials will be based on ASSIST or the Talk to Frank website and as a result are in line with the current, widely publicised UK governmental guidelines.

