#### **Process** evaluation

Following the framework proposed by Steckler and Linnan (2002)(25) the process evaluation will address the following issues:

Fidelity: The process evaluation will assess whether training of peer supporters was delivered as intended, and how frequently conversations on drug use between peers occurred. Semi-structured interviews with ASSIST+Frank and Frank friends trainers (n=4), focus groups with peer-supporters (n=4) and structured observation (n=4) will be used to explore variation in training and the interaction between the schools' contexts and delivery by PHW staff. A documentary analysis of peer-supporters diaries will also be used to assess how frequently conversations are reported, and the topic of these conversations. Data will be compared and contrasted across respondents and schools to explore potential variation. Measures of fidelity will be used in secondary analysis of primary and secondary measures to explore programme pathways and refine the programme logic model.

Feasibility and acceptability: The feasibility and acceptability of delivering ASSIST+Frank and Frank friends will be examined via semi-structured interviews with trainers (n=4), peer supporters (n=24), school staff (n = 12) and a focus group with parents (n=6). Another important aspect of examining acceptability will be to assess the existing provision of drug-focused education or interventions in both intervention and control schools via focus groups with school SMT members (n=5). Approximately a third of the focus groups with staff and parents will take place in each trial arm to assess trial acceptability. Interviews with PHW staff (n=2) and members of the Area Planning Board for Substance Misuse in Cardiff, a multi-agency group tasked with implementing Welsh Government policy (n=2) will explore national and local implementation issues.

*Programme reach and reception:* A random sample of peer supporters (n=12) will be interviewed in schools which have the highest and lowest incidence of drug use. With information on FSM entitlement, parental social class and other demographic variables, we will explore evidence of and reasons for variation in the receipt of ASSIST+Frank.

Sustainability: The interviews with trainers and teachers in intervention schools and PHW staff will examine what structures and resources need to be in place for sustained implementation by schools and facilitate a definitive trial.

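### School-retention criterion 7(b) counts 9 schools in a trial that randomises 12, so whether a whole comparison arm may be lost depends on how it is read

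*Protocol*

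**What the plan says.** Protocol section 6 describes an "Exploratory 4-arm trial with cluster randomisation (at the level of school) in 12 state secondary schools in South Wales". Section 9.6 fixes the allocation: "Schools will be randomly assigned to one of the 4 arms with an assignment ratio of 3: 3: 3: 3". The Design paragraph of section 3.3 lists the arms: "ASSIST in year 8 with ASSIST+Frank adjunct intervention in year 9; ASSIST in year 8 only; Frank friends in year 9 only; usual care comparison".

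Section 8.1 sets the progression criteria. Item 1 asks "Was it feasible to implement the ASSIST+Frank intervention in (at least) 2 out of 3 intervention schools" and item 2 asks "Was it feasible to implement the Frank friends intervention in (at least) 2 out of 3 intervention schools", so each of the two new interventions has three schools. Item 7 covers the trial design and methods and has three parts, joined by *and*. Part (b) is the only school-retention threshold: "a minimum of 5 out of 6 intervention schools and 2 out of 3 schools from the comparison arms" are to take part in the 18-month follow-up. Part (c) sets student response at 80% or more at baseline and 75% or more at follow-up.

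Section 11.1.4 says of the usual-care arm: "The three schools that do not receive ASSIST, ASSIST+Frank or Frank friends will continue" as before.

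**The concern.** The six intervention schools are clear: three ASSIST+Frank and three Frank friends. That leaves six schools in the other two arms, yet 7(b) gives three as the denominator while writing *arms* in the plural. Three randomised schools are unaccounted for unless the reader supplies a word that is not there.

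The primary aim (section 5.1) is to decide whether to go on to a full-scale trial, and retention is a stated objective (section 5.2). Both comparison arms are needed for the contrasts in section 15.1. Usual care enters three of the four: against ASSIST, against ASSIST+Frank and against Frank friends. ASSIST only enters two: against usual care and against ASSIST+Frank. A retention rule that might or might not tolerate the loss of one of these arms is a poor basis for calling a four-arm design feasible.

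**Working it through.** **Inputs.** 12 schools (section 6); four arms at 3:3:3:3 (section 9.6); three schools in each new-intervention arm (section 8.1, items 1 and 2); three usual-care schools (section 11.1.4); hence three ASSIST-only schools.

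**Design count.** 4 × 3 = 12, which reproduces the stated number of schools.

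**Criterion count.** 6 + 3 = 9, and 12 − 9 = 3 schools are not covered.

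**Can another classification of the arms repair it?**
- Intervention = the two Frank arms: 3 + 3 = 6, as stated. The comparison arms then hold 3 + 3 = 6, not 3.
- ASSIST also counted as an intervention: 3 × 3 = 9 intervention schools, not 6. Section 8.1 assesses only the two new interventions, so this reading is weak anyway.
- Comparison = usual care alone: the 3 is right, but the plural is wrong and nothing covers ASSIST only.

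**What each reading permits.** Let each arm keep 0 to 3 schools, giving 4⁴ = 256 patterns, and require at least 5 of the 6 Frank schools throughout.

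| Reading of the comparison part | Fewest schools meeting 7(b) | Whole comparison arm can be lost? |
|---|---|---|
| Any 2 comparison schools | 5 + 2 = 7 of 12 (58%) | Yes, either one |
| 2 of 3 usual-care schools only | 5 + 2 = 7 of 12 (58%) | Yes, ASSIST only |
| 2 of 3 in each comparison arm | 5 + 2 + 2 = 9 of 12 (75%) | No |
| Two thirds of the six, i.e. 4 of 6 | 5 + 4 = 9 of 12 (75%) | No |

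Under every reading the 5-of-6 part protects both Frank arms, because losing one leaves at most three.

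**Two results that show the ambiguity.**
- All 6 Frank, 3 ASSIST-only and 0 usual-care schools retained: 7(b) passes on the first reading and fails on the other three.
- 5 Frank, 0 ASSIST-only and 3 usual-care schools retained: 7(b) passes on the first two readings and fails on the last two.

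**Illustration of how far the readings differ.** Assume each school stays independently with the same probability. The protocol gives no such figure, so a range is shown. The chance of meeting 7(b) is P(at least 5 of 6 Frank schools) × P(comparison part).

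| Probability that a school stays | Any 2 | Usual care only | 2 of 3 in each | 4 of 6 |
|---|---|---|---|---|
| 0.7 | 0.42 | 0.33 | 0.26 | 0.31 |
| 0.8 | 0.65 | 0.59 | 0.53 | 0.59 |
| 0.9 | 0.89 | 0.86 | 0.84 | 0.87 |

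**Interaction with 7(c).** Suppose follow-up response is counted over all students in 12 schools of equal size. Keeping 9 schools caps it at 9/12 = 75%, keeping 8 at 8/12 = 66.7% and keeping 7 at 7/12 = 58.3%. On that denominator 7(c) fails with 7 or 8 schools. With 9 it passes only if every student in the remaining schools responds. If response is counted within participating schools, 7(c) gives no such protection. The protocol does not say which.

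**The case against.** The best defence is that 7(b) means two of three in each comparison arm. Three is the size of one arm, the plural fits, and items 1 and 2 of section 8.1 already use two of three as a per-arm threshold. The denominators are then 6 + 3 + 3 = 12 and no arm can be lost. This reading is plausible and may be what was intended. It still needs the word *each*, and the same sentence pools the two Frank arms as six, so the text does not settle it.

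The any-two reading has its own flaw: it is really 2 of 6, which contradicts the stated 3. The usual-care-only reading gets some support from section 3.3, which attaches the word comparison to usual care, but it leaves the plural unexplained.

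It is also fair to say that 7(c) may act as a backstop, that the steering committee has still to agree the criteria, that numbers of schools retained will be reported, and that no estimate in this unpowered exploratory trial depends on the phrase. These points limit the severity. They do not make the count right.

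A reader might also infer that the criterion is left over from a three-arm design. Section 13.3 says "Approximately a third of the focus groups with staff and parents will take place in each trial arm to assess trial acceptability", and section 14.1 lists 408 three times although 1632/408 = 4 and the synopsis lists four arms. That origin is possible but not shown. The focus-group sentence is approximate, concerns qualitative sampling, and is a separate minor wording point.

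**Conclusion.** Criterion 7(b) is wrong as written, with moderate severity. Its denominators total 9 against 12 randomised schools, and the minimum it implies is 7 of 12 (58%) or 9 of 12 (75%) depending on the reading. The count rests only on the 3:3:3:3 allocation and on the two Frank arms being the six intervention schools.

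Three stronger conclusions are tempting, and the document does not support them:
- That the rule definitely tolerates the loss of a comparison arm. It does so on two readings and not on the per-arm or 4-of-6 readings.
- That it can be met with no usual-care schools left. This needs the any-two reading, or comparison taken to mean ASSIST only. If comparison means usual care, at least two of those schools must remain.
- That the trial could be judged feasible with 7 of 12 schools. Item 7 also requires 7(c), which would fail if response is counted over all 12 schools of similar size. Because that denominator is unstated, 7(c) can be neither relied on nor dismissed.

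**What to change.** Restate 7(b) so that it covers all 12 schools and names each arm. For example: at 18 months, at least 5 of the 6 ASSIST+Frank and Frank friends schools, at least 2 of the 3 ASSIST-only schools and at least 2 of the 3 usual-care schools take part. That requires at least 5 + 2 + 2 = 9 of 12 schools and rules out the loss of any whole arm. If the investigators intend a different threshold, they should state it with the arms and denominators named.

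It would help to state in 7(c) whether follow-up response is counted over all students in the 12 randomised schools or only in those still taking part.

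The cost is one sentence for 7(b) and a short phrase for 7(c), agreed with the Trial Steering Committee before follow-up data are seen. No extra data are needed.

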#### 8.2 Pilot primary outcome measure

Incidence of any illicit drug use assessed by self-report questionnaire 18 months after randomisation.

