#### Aims

The primary aim of this project is to develop, pilot and assess the feasibility, acceptability and delivery of two new, informal peer-led interventions designed to prevent illicit drug use among secondary-school students, as well as to assess trial recruitment and retention rates. We will evaluate the effect of these peer-led drug and a peer-led smoking intervention on the: incidence of drug use (primary outcome); the frequency of use of any and specific drugs; cannabis dependence; incidence of smoking; smoking frequency; nicotine dependence; and alcohol use. These data will not provide any indication of effectiveness but will give an indication of trial feasibility, effect-sizes, and potential mechanisms of action to inform the design of a definitive phase three trial.

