#### Outcome measures

Within the exploratory trial, a mixed methods process evaluation will be used to assess each intervention against pre-defined progression criteria (to be agreed by the Trial Steering Committee) based on: 1) the feasibility of delivering ASSIST+Frank and Frank friends; 2) the acceptability of ASSIST+Frank and Frank friends to peer supporters; 3) the acceptability of the interventions to school senior management teams, other school staff, and parents; and 4) acceptability of trial design and assessment methods. Numbers of schools and participants recruited and retained will be presented as well as data on intervention fidelity. The indicative primary effectiveness outcome will be the incidence of any drug use assessed 18 months post randomisation. Secondary outcomes include the frequency of use of any and specific drugs; cannabis dependence; smoking frequency; nicotine dependence; and changes in social networks of peer drug and tobacco use.

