#### 14 Statistical considerations

#### 14.1 Sample size

The total sample size of 12 schools for the exploratory trial is anticipated to equate to approximately 2040 students (assuming a 170 pupils in a year), which with a response rate of 90% (based on 1-year follow-up in the RCT of ASSIST (10), will achieve a sample of 1632 students (408; 408; 408 per arm). If the average year group had 150 students, we would expect 1800 to be sampled; 1440 respond with an 80% response rate, equating to 360 per arm. The choice of 12 schools will provide some information on variability within and between schools at baseline and follow-up. This sample is not anticipated to provide adequate

power to detect a statistically significant difference across groups, as this is an exploratory trial. However, the sample will indicate the likely response rates, and permit estimates (with 95% confidence intervals) of likely effect sizes, and intra-cluster correlations (ICCs) of drug incidence in each group in anticipation of a larger trial.

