## 15 Analysis

### 15.1 Main analysis

The statistical analyses will be primarily descriptive, providing a realistic estimate of eligibility, recruitment, intervention delivery and retention rates in the study population. We will analyse key secondary outcomes that are more immediate targets of the intervention (e.g. knowledge of the harms of drug use; mean peer level drug use) to consider the potential of the intervention. We will undertake mediator analysis to see if the identified pathways in the logic model are associated with the uptake of drug use. Individuals lost to follow-up will be compared to those who complete follow up to identify any potential biases.

An intention to treat (ITT) analysis will compare the prevalence of any drug use across the 4-arms using a two-level logistic regression model to account for clustering within schools. The main analysis will examine prevalence of any drug use at 18 months. The baseline prevalence of any drug use, as well as age, sex, free school meal entitlement, and family affluence will be included as covariates. As an exploratory trial the proposed analysis is not powered to provide a definitive comparison between the intervention and control groups and as such p-values will not be presented. An exploratory analysis will nevertheless be undertaken. We will model comparisons between: a) ASSIST and the usual care control (to examine any unintended effects of ASSIST on drug use), b) ASSIST+Frank and the usual care control, c) Frank friends and the usual care control, and d) ASSIST and ASSIST+Frank to estimate the added value of the Talk to Frank content. These key trial parameters will inform the power calculations for a future definitive trial.

Between-group comparisons for secondary outcomes will be modelled similarly using either linear (e.g. frequency of drug use) or logistic (e.g. cannabis dependence) regression models with the focus on 95% confidence intervals to estimate possible effect sizes.

Exploratory analysis will consider the impact of demographic factors as well as other theoretical moderators on the intervention effect using interaction terms included in the main

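### The primary outcome is incidence of drug use, but the main arm comparison is of prevalence in all students, with recall window and level of the baseline covariate unstated

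*Protocol*

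**What the plan says.** The protocol names incidence as the primary effectiveness outcome in three places. Section 8.2 gives it as "Incidence of any illicit drug use assessed by self-report questionnaire 18 months after randomisation". The study summary (section 3.3, Outcome measures) says "The indicative primary effectiveness outcome will be the incidence of any drug use assessed 18 months post randomisation", and the Aims paragraph of the same summary also labels incidence of drug use as primary. Section 14.1 promises "intra-cluster correlations (ICCs) of drug incidence in each group" to help plan a larger trial.

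Section 15.1 describes a different quantity: "An intention to treat (ITT) analysis will compare the prevalence of any drug use across the 4-arms using a two-level logistic regression model". It then states: "The main analysis will examine prevalence of any drug use at 18 months". On adjustment it says: "The baseline prevalence of any drug use, as well as age, sex, free school meal entitlement, and family affluence will be included as covariates". Four pairwise arm contrasts follow, and the section closes the topic with "These key trial parameters will inform the power calculations for a future definitive trial".

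Nothing in 15.1 restricts the model to students who had not used drugs at baseline. Section 15.2 plans a sub-group of baseline ever-users, so such students are in the sample. Section 8.3 collects four recall windows (ever, 12 months, 30 days, past week), but neither 8.2 nor 15.1 says which of them defines any drug use. Section 15.1 does not say whether baseline prevalence enters as each student's own answer or as a school figure.

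**The concern.** Incidence counts new users among those who had not used before. Prevalence counts everyone who reports use, whether they started during the trial or earlier. The protocol fixes the outcome in one section and the model in another, and the two disagree. An analysis plan could follow one only by departing from the other.

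What is at stake is planning. Section 5.2 lists effect sizes and an appropriate sample size for a definitive trial among the objectives, and 15.1 says its estimates will feed that power calculation. If the definitive trial takes incidence as its outcome, its control rate, effect size and intra-cluster correlation should all refer to incidence. As written, the control rate and effect come from a prevalence model, while section 14.1 promises the intra-cluster correlation for incidence.

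**Working it through.** **The plan's own figure.** 12 schools × 170 pupils = 2040; × 0.80 = 1632; ÷ 4 = 408 per arm, which matches the Synopsis. (Section 14.1 prints 90% beside the same 1632; 90% would give 1836, or 459 per arm. That is a separate discrepancy and does not affect this point.) No power, effect size or drug-use rate is stated.

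**Assumed inputs.** The protocol gives none of these:
- baseline use b = 3%, 5%, 10%
- 18-month incidence among baseline non-users in the control arm i = 5%, 10%, 15%
- true incidence odds ratio (OR) 0.60
- share r of baseline users who report use at follow-up: 100% (lifetime use, consistent reports), or 60% (recent-use window or inconsistent reports)

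The calculation uses expected counts in a single-level logistic model with arm and baseline use. School effects and the other covariates are left out.

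**Formula.** Prevalence at 18 months = b × r + (1 − b) × incidence.

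**Worked case: b = 5%, i = 10%.** Control odds of incidence are 0.10/0.90 = 0.1111. Multiplied by 0.60 this is 0.0667, so intervention incidence is 0.0667/1.0667 = 6.25%.

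1. *Incidence among baseline non-users.* OR 0.60, on 0.95 × 408 ≈ 388 students per arm.
2. *Crude lifetime prevalence, r = 100%.* Control: 0.05 + 0.95 × 0.10 = 14.5%. Intervention: 0.05 + 0.95 × 0.0625 = 10.94%. OR = (0.1094/0.8906)/(0.145/0.855) = 0.72. The control event rate is 14.5%, against 10% for incidence.
3. *Prevalence adjusted for the student's own baseline use, r = 100%.* Every baseline user is positive at follow-up in both arms, so that stratum carries no information on arm. The adjusted OR is 0.60, identical to incidence.
4. *Same adjustment, r = 60%, no effect in baseline users.* A Mantel–Haenszel check on 408 per arm:
   - Non-users (387.6 per arm): 24.225 × 348.84/775.2 = 10.90, and 363.375 × 38.76/775.2 = 18.17.
   - Baseline users (20.4 per arm): 12.24 × 8.16/40.8 = 2.45 in both numerator and denominator.
   - OR = 13.35/20.62 = 0.65. The logistic fit also gives 0.65.
5. *As 4, but the intervention has the same OR of 0.60 in baseline users.* The adjusted OR is 0.60 again.

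**Over the whole grid, true incidence OR 0.60:**

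| Quantity | OR |
|---|---|
| Incidence among baseline non-users (about 367–396 per arm) | 0.60 |
| Prevalence, own baseline use adjusted, lifetime and consistent | 0.60 |
| Prevalence, own baseline use adjusted, r = 60%, no effect in users | 0.62–0.74 |
| Crude prevalence, lifetime and consistent | 0.66–0.86 |

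With a true incidence OR of 0.75 the last two rows become 0.76–0.84 and 0.79–0.91. The crude row is the reference for a school-level baseline covariate, which would not fully remove the contribution of individual baseline users.

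**The case against.** The strongest reply is that the planned model is adjusted. If any drug use means lifetime use, reports are consistent and the covariate is the student's own answer, the prevalence model returns exactly the incidence odds ratio. That is correct. A reader might infer that baseline users necessarily dilute the effect, or that the model will fail because baseline use predicts the outcome perfectly. The documents support neither. In that case dilution is zero, and separation affects only the baseline-use coefficient, a nuisance term. The crude range describes a model the protocol does not plan and only bounds what a school-level covariate might leave. What remains of the concern is that the protocol does not state the conditions that would make the two quantities agree.

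A reader might also infer that incidence is never analysed. That is too strong: section 14.1 plans its intra-cluster correlations, and section 15.2 plans exploratory associations of incidence with sex, family affluence, smoking status and peer networks. Only the comparison between arms is missing.

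It can further be said that incidence is nowhere defined and may be loose wording, and that a recall window is commonly left to an analysis plan. Both are fair, and they are why the outcome could be renamed instead of the model changed. They do not remove the conflict, because the protocol itself fixes both the outcome and the model.

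Finally, the primary aim is feasibility and acceptability, no progression criterion in 8.1 uses a drug-use result, and 15.1 presents no p-values. This stands, and it lowers the severity.

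**Conclusion.** The mismatch is real: sections 3.3 and 8.2 declare incidence, section 14.1 promises intra-cluster correlations of incidence, and section 15.1 compares baseline-adjusted prevalence across arms in all students. No arm comparison of incidence is specified, and the window and covariate level that would settle the matter are absent.

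The effect on the odds ratio ranges from nil to material. It is nil with lifetime use, consistent reports and the student's own baseline answer. It is also nil with individual adjustment if the intervention acts equally, on the odds ratio scale, on baseline users and non-users. Otherwise, if baseline users are unaffected, a true 0.60 appears as about 0.62–0.74 with individual adjustment. With a school-level covariate it could move towards the crude 0.66–0.86. These figures rest on assumed rates and illustrate direction and scale only.

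The lifetime-prevalence event rate exceeds incidence whenever there are baseline users and reports are consistent (14.5% against 10% in the worked case). The intra-cluster correlation is likewise a different quantity; the documents give no basis for its size. Severity is moderate: the trial is exploratory and no progression criterion depends on drug use, but these estimates are meant to inform the size of the definitive trial.

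**What to change.** Preferred change, in section 15.1: make the main arm comparison first-ever use reported at 18 months among students who reported no lifetime use at baseline. Drop baseline use as a covariate and keep age, sex, free school meal entitlement and family affluence. Report the control event rate and the intra-cluster correlation for that same outcome. Keep prevalence in all students as a secondary analysis, with a stated recall window and adjustment for each student's own baseline response to the same item. Define incidence in 8.2 in the same terms.

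Alternative: redefine the primary outcome as prevalence, with a stated recall window and covariate level, and align the summary (Aims and Outcome measures), 8.2, 14.1 and 15.1.

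The cost is wording, since 8.3 already collects lifetime use. Under the preferred change, baseline ever-users (about 12–41 of 408 per arm at 3–10% baseline use) and students without baseline data leave the main analysis set; those who complete follow-up still count in the prevalence analysis where its adjustment allows. Students are still compared as randomised, because the restriction uses an answer that section 9.6 places before allocation. Section 13.5, which appears to place baseline after randomisation and delivery, should be reconciled with 9.6 for this to hold.
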